5.2 Exclusion Criteria

The primary objective is to validate DSI 18.3 to "Rule Out" large esophageal varices. Our prior studies of the distribution of DSI by stage of liver disease have demonstrated increasing DSI with increasing stage of fibrosis and increasing CP class of cirrhosis (unpublished data). Patients with CP class C cirrhosis have up to an 85% prevalence of esophageal varices, and clear indications for EGD to evaluate for varices, independent of DSI result. For these reasons, CP class C cirrhosis is an exclusion to participation. The performance of DSI in CP class C cirrhosis might be a focus for future study and consideration.

The primary endpoint for this study is the endoscopic finding of large esophageal varices. Given this endpoint, a prior known endoscopic diagnosis of large esophageal varices, variceal hemorrhage, or treatment of varices are exclusions to participation.

The Exclusion Criteria are:

- Unable to give informed consent
- Unable to obtain venous access for administration of intravenous cholate
- Unable to absorb orally-administered cholate (examples could include underlying severe gastroparesis or having undergone extensive small bowel resection, conditions or post-operative state that could impair the absorption of the orally administered d4-cholate)
- Known hypersensitivity to human serum albumin
- Known hypersensitivity to any of the components of the HepQuant SHUNT Liver Diagnostic Kit
- Acute hepatitis, Acute Liver Failure, or Acute on Chronic Liver Failure
- Acute drug-induced liver disease (DILI)
- Noncirrhotic causes for portal hypertension and varices

- Ongoing active alcoholic hepatitis
- Child-Pugh class C defined by Child-Pugh score 10 or higher
- Dialysis
- Active infection or febrile illness within the last month
- Documented history of esophageal or gastric variceal hemorrhage
- Documented history of treatment of varices
- Documented history of endoscopic findings of large esophageal varices
- Hepatocellular carcinoma beyond Milan or UCSF criteria
- Thrombosis of main portal vein
- Liver transplant recipient
- Pregnancy
- Women who are breast-feeding
- Serious intercurrent medical or surgical illness, such as acute myocardial infarction, acute cerebral hemorrhage, sepsis, or other immediate life-threatening illness
- NPO (nothing through the mouth) status

5.3 Lifestyle Considerations

There are no restrictions regarding smoking or use of tobacco or marijuana products, concomitant drugs, over-thecounter products, medications, or ongoing alcohol use, except for the case of alcoholic hepatitis (see below). There are no dietary restrictions or restrictions on daily activity.

Patients with acute hepatitis, acute liver failure, or those with ongoing active alcoholic hepatitis are excluded to avoid confounding the relationship of DSI to varices risk by including patients with severe hepatocellular dysfunction.

5.4 Screen Failures

Screen failures are defined as participants who consent to participate in the study but do not subsequently undergo either the HepQuant SHUNT Test or the EGD, or for some other reason are not entered into the study (due to travel, medical illness, death, or other reason). HepQuant will comply with collecting a minimal set of screen failure information which is required to ensure transparent reporting of screen failure participants, to meet the Consolidated Standards of Reporting Trials (CONSORT) publishing requirements and to respond to queries from regulatory authorities. The minimal information will include demography, screen failure details, eligibility criteria, and any serious adverse event (SAE).

Individuals who do not meet the criteria for participation in this trial because of a travel, family emergency, or other modifiable reason may be rescreened. In case of Rescreening, the number for the original screening should not be re-used. Create a NEW subject ID number for any rescreened subject.

5.5 Strategies for Recruitment and Retention

Anticipated Accrual Rate:	Up to 40 clinical sites enrolling 5 to 10 patients per month Overall, the study should be completely enrolled over 20 to 24 months
Source of participants:	Outpatient clinics Patients will be identified by their care provider by:

- Diagnosis of CLD,
- Etiology of CLD, and
- In process of scheduling for EGD

The SHUNT-V Study for Varices Protocol HQ-US-SHUNT-1801	Version 2.4 6 October 2020
	The study coordinator will be notified by the care team.
	The study coordinator, principal investigator, or subinvestigators will then meet with the patient for consent.
Recruitment venues:	Communications with referring clinics and care providers Posted notices in clinics
Recruitment Strategies:	Notices to care providers Posted notices in GI and Liver Clinics Brochures to patient advocacy groups Local advertisement Social Media
Long-term Participation:	Not applicable

Recruitment of women and minorities: Because CLD is more common in men, we expect a greater proportion of men to be enrolled. However, women are not restricted in terms of enrollment – in the USA about 40% of cases of CLD are women. Likewise, the study is not restrictive of race or ethnicity. We expect enrollment to reflect the distribution of gender and race/ethnicity as shown above.

Inclusion of Vulnerable participants: Not applicable.

Compensation and Incentives: A single payment will be made to the participant for completion of all procedures and visits. There are 3 unique study-related visits (excluding the EGD that is considered to have been ordered as part of the patients non study-related care). Payments will be prorated for participants by the number of study visits completed.

6 STUDY INTERVENTION

6.1 The HepQuant SHUNT Liver Diagnostic Kit (HepQuant SHUNT Test)

The HepQuant SHUNT Liver Diagnostic Kit contains two forms of cholate labeled with stable isotopes as molecular probes to quantify global liver-specific function and the portal circulation. A complete description can be found in the Instructions for Use (IFU) in **Appendix C** and Investigator's Brochure in **Appendix B**.

Cholate as a Molecular Probe. Cholate has several characteristics that favor its use as a molecular probe of the hepatic and portal circulations:

- Cholate is efficiently absorbed from the intestine.
- Cholate has a 70 to 80% first-pass hepatic extraction.
- Cholate is not metabolized, nor does it affect metabolism in the doses used in the HepQuant SHUNT test.
- Cholate is endogenous to the human body and, therefore, has none of the risks associated with xenobiotic exposure.
- Cholate in a dose of 15 mg kg⁻¹ d⁻¹ is FDA-approved for therapy of rare forms of pediatric liver disease.
- Clinical Trials Grade and GMP Grade Cholate are commercially available for purchase as a single carbon-13 label, [24-¹³C]cholate (13C-cholate), and as a tetra-deuterium label, [2,2,4,4-²H]cholate (d4cholate).

• The deuterium-tagged internal standard is commercially available for use in the laboratory as an internal standard for quantification of cholate species by LC/MS.

The HepQuant SHUNT Liver Diagnostic Kit. The HepQuant SHUNT test is provided as test kits that are shipped to a testing center. At the testing center, the test compounds are administered and blood samples collected over 90 minutes. The sera from the timed blood samples are separated and shipped to a qualified laboratory for quantifying cholate concentrations, calculating test parameters, and reporting results. The kit contents include:

- Sealed vial of sterile solution of d4-cholate (40 mg in 10 mL sodium bicarbonate) for oral use
- Sealed vial of sterile solution of 13C-cholate (22 mg in 5.5 mL sodium bicarbonate) for intravenous use
- Sealed vial of 20 mL of 25% human serum albumin for intravenous use 5 mL is added to 5 mL of the 13C-CA solution prior to intravenous injection
- Pipettes
- 6 transfer tubes (for transport of serum to HepQuant designated lab)
- 3-way stopcock
- Labels
- Instructions for Use (IFU)
- Test Requisition Form (TRF)Mailer

6.2 Test Outputs

6.2.1 SYSTEMIC HFR

The intravenous clearance (Cl_{iv}, mL min⁻¹) is defined as the dose/AUC for 13C-cholate. The Systemic Hepatic Filtration Rate (Systemic HFR) is defined as the Cl_{iv} per kg of body weight and is expressed as mL min⁻¹ kg⁻¹.

6.2.2 PORTAL HFR

The apparent oral clearance (Cl_{oral}, mL min⁻¹) is defined as the dose/AUC for d4-cholate. The Portal Hepatic Filtration Rate (Portal HFR) is defined as the Cl_{oral} per kg of body weight and is also expressed as mL min⁻¹ kg⁻¹.

6.2.3 SHUNT

SHUNT, the portal-systemic shunt fraction, is calculated as the ratio Systemic HFR/Portal HFR x 100%.

6.2.4 DSI

The calculation for Disease Severity Index is a proprietary formula derived from Systemic HFR and Portal HFR. DSI 0 implies no hepatic impairment and is based on the means (+3 SDs) for Systemic and Portal HFRs of normal weight healthy volunteers. DSI 50 represents severe hepatic impairment as measured in terminally ill CP (Child-Pugh) C cases with clinically advanced liver disease. Subjects with intermediate severity of liver disease have intermediate DSI scores.

6.2.5 STAT

STAT is defined as the 60-minute 4D-CA concentration normalized to an ideal body weight of 75 kg. STAT was found in previous studies to correlate closely with DSI ($r_2 = 0.88$). Utilizing this single time point will also be evaluated as a simplified testing approach.

6.3 Documents, Instructions, and Brochures

Investigator Agreement: Investigator Brochure: Instructions for Use: Proposed Labeling: Material Safety Data Sheet:	See Appendix A. See Appendix B. See Appendix C. See Appendix D. See Appendix E.
Informed Consent Form:	See Appendix F.
Self-Reported Subject Tolerability Su	rvey: See Appendix G.
Risk classification:	Significant risk device, Class III
Commercial availability:	For investigational use only. Not for commercial sale or distribution.
Device size:	9 x 6.5 x 2.75 inches
Device model:	SHUNT
Components:	See IFU and Labels, Appendices C & D, Respectively

Duration of exposure: In our studies, we have measured the clearance rates for IV 13C-cholate removal from the blood. The k_{elim} of the first phase of clearance of IV 13C-cholate ranges from approximately 0.10 min⁻¹ in healthy persons or persons with minimal liver disease, to approximately 0.05 min⁻¹ in persons with advanced liver disease. There is a second slower phase of clearance, which contributes little to overall clearance in healthy persons. But, in persons with liver disease, the second phase contributes increasingly to overall clearance as liver disease worsens due to impaired hepatic uptake of cholate and portal-systemic shunting. In healthy persons or persons with minimal liver disease, the half-life of clearance of cholate from the blood is 7 to 10 minutes; cholate is completely eliminated from the blood within 35 to 50 minutes. In advanced liver disease, complete elimination of cholate from blood may take hours.

The 13C- and d4-cholates enter the body's cholate pool and are cleared based on turnover rate of the cholate pool. The turnover of the cholate pool is approximately 0.3 d⁻¹ or $t_{1/2}$ of 2.3 days. The cholates are completely removed from the body after 12 days (5 half-lives).

Frequency of exposure: Once

6.4 Dosing and Administration

Time of Day: The HepQuant SHUNT Test is usually administered in the morning after an overnight fast. The Test may also be administered anytime during the day if the subject has fasted for at least 5 hours.

Duration of Administration of Cholates. The administration of the 13C-cholate intravenously in combination with the d4-cholate orally takes 1 minute.

Routes of Administration:	13C-cholate	Intravenously
	d4-cholate	Orally

Test administration is described in the Instructions for Use (IFU, **Appendix C**). A winged (or "butterfly") infusion or blood collection set or an intravenous catheter will be placed in one arm for administration of the 13C cholate, then removed following administration. An indwelling intravenous catheter is placed in the opposite arm for blood sampling. For subjects in which access cannot be obtained in both arms, the administration and sampling can occur in through a single indwelling catheter, provided adequate flushing is performed post-administration per the IFU. 13C-cholate, 20 mg (fixed dose), in sterile sodium bicarbonate solution is mixed with 5 mL of 25% human serum albumin prior to injection, and then injected intravenously over one minute. Simultaneously, d4-cholate, 40 mg

(fixed dose), in sterile sodium bicarbonate solution, is administered orally. Blood is sampled from the peripheral venous catheter at baseline and subsequently at 5 ± 1 , 20 ± 2 , 45 ± 5 , 60 ± 5 , and 90 ± 5 minutes post-dosing. The clearances of both 13C- and d4-cholate are measured from the timed blood samples.

Minimum Doses:	13C-cholate	Fixed Dose, Intravenous	20 mg
	d4-cholate	Fixed Dose, Oral	40 mg
Maximum Doses:	13C-cholate	Fixed Dose, Intravenous	20 mg
	d4-cholate	Fixed Dose, Oral	40 mg

Dose Escalation: NA

Hold Times: The HepQuant SHUNT Liver Diagnostic Kits are held or stored at ambient temperature. Once the 13C-cholate has been mixed with the 25% human serum albumin or the d4-cholate vial has been opened the Test must be administered within 4 hours.

6.5 Preparation/Handling/Storage/Accountability

6.5.1 ACQUISITION AND ACCOUNTABILITY

How Kits will be Provided to the Investigator. The HepQuant SHUNT Liver Diagnostic Kits will be shipped in sealed containers. Within each container is a temperature indicator that ensures the temperature of the internal contents of the shipping container have been appropriately controlled.

Distribution of Kits. The HepQuant SHUNT Liver Diagnostics Kits are assembled by Prospect Life Sciences, Westminster, CO, who ships the containers with the Kits directly to clinical testing centers. The Kits will be loggedin when received and stored in secure environment under lock and key. In some centers, the Kits will be sent to a research pharmacist who will be responsible for receiving and securing the Kits. In others, the Kits will be sent to the study coordinator who will be responsible for receiving and securing the Kits. The details of acquisition and storage are delineated in the IFU (Appendix C).

6.5.2 FORMULATION, APPEARANCE, PACKAGING, AND LABELING

NOTE: Additional details may be found in **Appendix B** (Investigator's Brochure), **Appendix C** (Instructions for Use), and **Appendix D** (Labeling).

Formulations. Sterile formulations of the labeled cholates, both 13C- and d4-cholate are supplied in clear glass vials. The labeled cholates are purchased in powder form and dissolved in 1M sodium bicarbonate solution (USP grade) to achieve concentrations of 4 mg/mL. The solutions are passed through 0.22-micron filters and undergo sterility and pyrogen testing. The absolute concentrations of d4-cholate and 13C-cholate are defined by LCMS methods – concentrations typically range from 3.5 to 4.2 mg/mL. Each vial of d4-cholate contains 40 mg in 10 mL 1M NaHCO₃ and each vial of 13C-cholate contains 22 mg in 5.5 mL 1M NaHCO₃. The vials are distributed in a HepQuant SHUNT Liver Diagnostic Kit and stored at ambient temperature.

A sterile glass vial of human serum albumin (25%, 20 mL, Grifols BLA STN 102478) is also contained within the HepQuant SHUNT Liver Diagnostic Kit.

NOTE: Although, the d4-cholate vial contains the exact volume, 10 mL, and amount of d4-cholate, 40 mg, the 13C-cholate vial for intravenous injection contains an excess volume, 5.5 mL, and amount, 22 mg, of 13C-cholate. The

excess is intentional, to provide sufficient "dead space" volume to allow for aspiration of exactly 5 mL of the 13C-cholate solution into a syringe. Accurate testing requires administration of the entire 10 mL of d4-cholate oral solution; and, exactly 5 mL of 13C-cholate intravenous solution.

Appearance:

Packaging: There is a $9 \times 6 \frac{1}{2} \times 2 \frac{3}{4}$ " outer kit box that contains a foil pouch envelope, which contains an ambient gel wrap holding the interior kit contents (test solutions, supplies). The kit boxes are shipped within a sealed cooler that is packaged within an outer shipping box.

Labeling: Each cooler box has a HepQuant identification label. Each kit has an outer label containing the contents, Use by Date, caution warnings of investigational use only and storage instructions. Tube labels are pre-filled for the site's convenience with places for protocol, subject ID numbers, date and timepoint of test. UN3373 Biological Substance Category B labels are included within each kit for return of samples.

Manufacturers: The 13C- and d4-cholate compounds raw materials used in the HepQuant SHUNT Liver Diagnostic Kit are manufactured by Sigma-Aldrich-Isotec (P/N's W3713 and W6829, respectively). The formulations of 13C- and d4-cholate in 8.4% sodium bicarbonate (Hospira, 80098EV) are manufactured by PINE Pharmaceuticals (P/Ns HQ-13C-ECG and HQ-d4-ECG), and the 25% human serum albumin was purchased from Grifols (BLA 102478), all other materials in the kit are sourced from commercial suppliers.

6.5.3 PRODUCT STORAGE AND STABILITY

Storage: The HepQuant SHUNT Liver Diagnostic Kit is stored at ambient temperature until ready for use in a room temperature environment. The product is securely stored at the clinical testing site.

Stability: The stability of the 13C- and d4-cholate solutions at ambient temperature has been verified by appearance, pH, isotope qualification, confirmation of sterility, pyrogen testing, particle analysis, color analysis, and purity checks by HPLC. The vial of 25% human serum albumin has a shelf-life at ambient temperature of 3 years.

Once a vial has been opened or solution removed from the vial, the solution must be used within 4 hours. If not used within 4 hours, it should be discarded.

6.5.4 PREPARATION

Upon opening the HepQuant SHUNT Liver Diagnostic Kit, the person administering the test will confirm clarity of all solutions and integrity of the Test Kit and its contents.

The HepQuant SHUNT test is performed after an overnight fast or after at least 5 hours of fasting during the daytime. Morning doses of ACE or ARB inhibitors, non-selective β-blockers (nadolol, timolol, propranolol), or other investigational drugs are held until after completion of the 90 minute HepQuant SHUNT test. Medications may be administered immediately following the drawing of the 90 minute blood sample. In these patients or subjects, or

in persons with known hypertension the blood pressure should be checked prior to test administration. The test should not be administered if the diastolic BP is 110 mmHg or higher. The test can be rescheduled once the blood pressure is controlled. The HepQuant SHUNT test requires peripheral venous access via a standard indwelling intravenous catheter. The injectable solution of 13C-cholate, 20 mg, dissolved in sodium bicarbonate and mixed with 25% human serum albumin (HSA), is administered over 1 minute. Simultaneously (during the 1 minute), the oral solution of d4-cholate, 40 mg, dissolved in sodium bicarbonate, is given as a quick bolus. The oral solution is mixed with flavoring or juice (apple or grape) for administration. A three-way stopcock is provided in the Kit to facilitate the mixing of 5 mL of 25% HSA with 5 mL of the 13C-cholate solution (20 mg 13C-cholate per 5 mL) in preparation for intravenous injection.

Albumin has 7 hydrophobic binding sites for cholate (107). The intravenous 13C-cholate solution is pre-mixed with human serum albumin (HSA) just prior to intravenous injection to bind cholate, maintain 13C-cholate in the intravascular space, and reduce risk of thrombophlebitis or phlebothrombosis at the injection site.

Within four hours of injection, exactly 5 mL of the 13C-cholate intravenous solution is mixed with 5 ml of the albumin solution (25% w/v human serum albumin (HSA), Albutein ®-25 from Grifols Therapeutic, Inc, BLA 102478). The vials of 25% HSA provided in the HepQuant SHUNT Liver Diagnostic Test Kit have a total volume of 20 mL; but, ONLY 5 mL is pre-mixed with the 13C-cholate in the syringe, 15 mL is discarded. The 13C-cholate/HSA mixture is injected intravenously through a winged (or "butterfly") infusion or blood collection set or an indwelling intravenous catheter over 1 minute as the d4-cholate solution is taken orally.

Blood samples are obtained via an intravenous catheter in the opposite arm at baseline and at 5±1, 20±2, 45±5, 60±5, and 90±5 minutes after dosing. The indwelling catheter is flushed with saline after each blood sample is obtained. The serum is separated and sent to the HepQuant laboratory for quantification of concentrations of endogenous cholate, d4-cholate and 13C-cholate.

Detailed Instructions For Use of the HepQuant SHUNT Test are provided in Appendix C.

6.6 Measures to Minimize Bias: Randomization and Blinding

Randomization:	Not a randomized trial	
Assignment to study groups:	Single Arm study	
Blinding:	 Triple-blind of HepQuant SHUNT Test results Patient Investigator and clinical center HepQuant 	

Single-blind of EGD results – HepQuant

Minimizing Bias: In the study the HepQuant SHUNT Test will be done prior to EGD, a sequence that is true for the clinic. The use of the HepQuant SHUNT test in this study mimics its intended use – i.e., a CLD patient meets sufficient clinical criteria to warrant EGD for screening or surveillance of varices. In the study, the enrolled subjects are scheduled for EGD, and meet these standard clinical criteria. In both the study, and for its intended use in the clinic, the HepQuant SHUNT test is administered after the clinical decision to perform EGD is made but prior to the performance of the EGD. The study results will be used to inform the clinician performing the EGD about the likelihood of large varices to aid in the decision to proceed or avoid the EGD.

Additionally, bias will be further minimized by blinding of patient, investigator and clinical center to the HepQuant SHUNT and DSI results; and, blinding of HepQuant to the EGD results.

Missing Data: Patients who have a DSI score but the EGD results are missing will be classified as "missing data". These patients are censored from the primary analysis which will only include the patients with both EGD results and DSI scores.

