6.7 Study Intervention Compliance

Assessment of adherence to Protocol: Adherence to the study protocol will be defined by the following processes and procedures:

- Monitoring by the CRO with ongoing review of eCRFs, observed versus expected
- Receipt of correct blood samples for standard laboratory tests
- Receipt of correct blood samples, dates, times for the samples used for the laboratory analysis of the HepQuant SHUNT Test
- Review of results of laboratory tests, dates, times
- Review of the TRF (Test Requisition Form)
- Review of the appearance and disappearance curves for 13C- and d4-cholate after their quantification to determine if sample times may have been switched
- Review of the completion of all study visits and procedures

The calculation of study intervention compliance will be determined by the formula:

% Compliance = (Observed DSI-EGD pairs) / (Expected DSI-EGD pairs) x 100%

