7 DISCONTINUATION AND WITHDRAWAL

7.1 Discontinuation of Study Intervention

Discontinuation related to administration of the HepQuant SHUNT Test, either prior to or during the Test administration, does not mean discontinuation from the study, and remaining study procedures should be completed as indicated by the study protocol. If a clinically significant finding is identified (including, but not limited to changes from baseline) after enrollment, the investigator or qualified designee will determine if any change in participant management is needed. Any new clinically relevant finding (aside from the findings from the EGD procedure) will be reported as an adverse event (AE).

The data to be collected will include the following:

- Reason for discontinuation
- Protocol-specified safety follow-up to capture adverse events (AE), serious adverse events (SAE), and unanticipated problems (UPs).

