7.2 Participant Discontinuation/Withdrawal from the Study

Participants are free to withdraw from participation in the study at any time upon request. An investigator may discontinue or withdraw a participant from the study for the following reasons:

- Pregnancy
- Significant study intervention non-compliance
- If any clinical adverse event (AE), laboratory abnormality, or other medical condition or situation occurs such that continued participation in the study would not be in the best interest of the participant
- Disease progression which requires discontinuation of the study intervention
- If the participant meets an exclusion criterion (either newly developed or not previously recognized) that precludes further study participation
- Participant unable to receive the HepQuant SHUNT Test
- Participant unable to receive the EGD within 42 days of the HepQuant SHUNT Tests

The reason for participant discontinuation or withdrawal from the study will be recorded on the "Withdrawal from Study" Case Report Form (CRF). Subjects who sign the informed consent form and are enrolled but do not receive the HepQuant SHUNT Test may be replaced. Subjects who signed the informed consent form, and are enrolled and received the HepQuant SHUNT Test but the EGD was not performed within 6 weeks of the HepQuant SHUNT Test will be replaced. The HepQuant SHUNT test results from these subjects will be censored and not included in the analysis of the study.

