9.3 Populations for Analyses

Population for Analysis: All enrolled subjects who underwent the HepQuant SHUNT Test; a maximum of N=420 and minimum of N=400 will be analyzed (the interim analysis will be conducted when DSI and EGD exam results are available in the analysis dataset for approximately N=250 participants).

Safety Analysis Dataset: All enrolled subjects who underwent the HepQuant SHUNT Test; a maximum of N=420 and minimum of N=250 will be analyzed.

- Per-Protocol Analysis: All enrolled subjects who completed the entire protocol
- Other Datasets that may be used for sensitivity analyses: None

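### Subjects with an EGD but no valid DSI would be dropped with no sensitivity analysis, so specificity may be overstated for the intended use

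*Combined protocol and SAP*

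**What the plan says.** Section 6.6 (Missing Data) describes one kind of incomplete subject, the one with a DSI but no EGD result. It then states the general rule, censoring these subjects from the "primary analysis which will only include the patients with both EGD results and DSI scores". The reverse case, an EGD without a DSI, is not discussed, but the rule removes it too. Section 9.5.1 is consistent with this reading, since it runs the final analysis on 400 subjects with complete data.

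Section 9.3 defines the analysis population differently: "All enrolled subjects who underwent the HepQuant SHUNT Test; a maximum of N=420 and minimum of N=400 will be analyzed". It does not say how a subject who underwent the test but has no DSI would be classified. It ends: "Other Datasets that may be used for sensitivity analyses: None".

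On how such subjects could arise, section 7.1 says: "Discontinuation related to administration of the HepQuant SHUNT Test, either prior to or during the Test administration, does not mean discontinuation from the study". The remaining procedures, which include the EGD, are still to be completed. Section 6.7 has the cholate curves reviewed "to determine if sample times may have been switched", but gives no rule for a test judged invalid. Its completeness measure is a single ratio of observed to expected DSI-EGD pairs, not split by cause or by varices status.

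Other provisions remove some of these subjects. Section 7.2 says: "Subjects who sign the informed consent form and are enrolled but do not receive the HepQuant SHUNT Test may be replaced". It also lists inability to receive the test as a reason for withdrawal. Section 5.4 classes consented subjects who do not undergo the test as screen failures.

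**The concern.** The intended use (section 1.1) is in patients already selected for EGD, where a DSI at or below 18.3 may support avoiding the procedure. A patient whose test gives no result gets no such support and stays on the path to EGD. For a rule-out test this has the same consequence as DSI > 18.3. Performance estimated only where the test worked therefore describes a more favourable population than the one that would start the test.

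Two quantities are exposed. Specificity is a reported measure, and section 9.4.2 gives it an acceptability floor of 0.28. The share of EGDs avoided is not an endpoint in section 3, but it is the main clinical argument for the test in sections 2.1.1, 2.2.4 and 9.5. The NLR, which carries the primary criterion, is exposed only if failure is related to varices. The plan has no step that would show whether it is.

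**Working it through.** **Inputs from the plan (section 9.2.1).** Sensitivity 0.90, specificity 0.50, prevalence 20%, so V = 80 with large varices and 320 without; NLR margin 0.52.

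**Reproducing the plan's figures.** Table 9, equation E, gives the variance of log NLR as 0.90/(0.10 × 80) + 0.50/(0.50 × 320) = 0.1125 + 0.003125 = 0.115625, so SE = 0.340.
- Power = Φ(ln(0.52/0.20)/0.340 − 1.96) = 0.802; Table 10 gives 0.80.
- Critical value = 0.52 × exp(−1.96 × 0.340) = 0.267; the plan gives 0.27.
- A simulation of the score test without the interim analysis gives 0.917 at NLR 0.20 and 0.017 at NLR 0.52; Table 12 gives 0.916 and 0.017.

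**Counting a failed test as not ruled out.** Let f1 be the failure rate with large varices and f0 the rate without. Both are assumptions.
- Sensitivity = 1 − (1 − 0.90)(1 − f1)
- Specificity = 0.50 × (1 − f0)
- NLR = 0.20 × (1 − f1)/(1 − f0)
- EGDs avoided = 0.20 × 0.10 × (1 − f1) + 0.80 × 0.50 × (1 − f0); with no failures, 0.02 + 0.40 = 0.42

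| f1 | f0 | Sensitivity | Specificity | NLR | EGDs avoided |
|---|---|---|---|---|---|
| 0 | 0 | 0.900 | 0.500 | 0.200 | 42.0% |
| 2% | 2% | 0.902 | 0.490 | 0.200 | 41.2% |
| 5% | 5% | 0.905 | 0.475 | 0.200 | 39.9% |
| 10% | 10% | 0.910 | 0.450 | 0.200 | 37.8% |
| 0 | 5% | 0.900 | 0.475 | 0.211 | 40.0% |
| 5% | 0 | 0.905 | 0.500 | 0.190 | 41.9% |

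The first row is also what the complete-pair analysis estimates in every scenario for sensitivity, specificity and NLR. Its share of EGDs avoided is also 42% when the two failure rates are equal.

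**Reach to the pass/fail rule.** With no failures among cases, moving the NLR from 0.20 to 0.27 would need f0 = 1 − 0.20/0.27 = 26%. Simulated power with 420 tested, a 95% score interval and no interim analysis:
- 5% failure in both groups: 0.916 dropping failures, 0.930 counting them.
- 5% in non-cases only: 0.923 and 0.907.
- 5% in cases only: 0.917 and 0.945.

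**A borderline example.** Take 80 cases with 10 missed and 320 non-cases, 16 of whom (5%) have no DSI, and apply the 96.07% score interval. Dropping the failures, the minimum passing count of true negatives is 132 of 304; counting them, it is 138 of 320. So 132 to 137 true negatives would pass only if failures are dropped. Now give the cases the same 5% rate, 4 of 80, again with 10 missed. The complete-pair analysis then has 10 missed of 76 and needs 138 of 304; counting failures still needs 138 of 320. The window closes.

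**The case against.** The strongest reply is that this hardly touches the primary conclusion. The criteria are the NLR and observed sensitivity. With equal failure the NLR does not move, and counting failures as not ruled out raises sensitivity, so dropping them is if anything conservative for that criterion. A reader might infer from the borderline example that the exclusion could turn a failing trial into a passing one. That requires failures concentrated in subjects without large varices and a result near the boundary. The documents give no reason to expect that pattern, and the opposite pattern would make the complete-pair NLR look worse than the counted one. This part of the reply stands.

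The number of such subjects may also be small. Section 5.2 excludes subjects without venous access or unable to absorb oral cholate. Sections 5.4 and 7.2 handle subjects who never receive the test through screen failure, withdrawal or replacement. A switched sample may be correctable, and section 6.7 does not say that it invalidates a test. So it cannot be said that such subjects will exist in any number, or that specificity is in fact overstated. Reasons for discontinuation are collected (section 7.1), so the problem is partly visible.

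What the reply does not answer is the subject whose test was started, gave no valid DSI, and who then had the EGD. Replacement does not answer it either: refilling to 400 complete pairs restores the sample size but still estimates performance only where the test worked.

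**Conclusion.** The point holds as a gap in the planned analyses. Following section 6.6 drops index-test failures, section 9.3 offers no sensitivity analysis that would show the effect, and the two sections disagree on the analysis set. The direction is clear for specificity, which is overstated to the extent that tests fail in subjects without large varices. EGDs avoided, if reported, is also overstated when failure is unrelated to varices. At an assumed 5% in both groups the effect is 2.5 points of specificity and about 2 points of EGDs avoided; at 2% it is about 1 point of each. Applied for illustration to HALT-C, 5% takes specificity from 106/195 = 0.544 to 0.516 and EGDs avoided from 107/217 = 49.3% to 46.8%.

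The documents do not support a claim that the primary result is biased in the test's favour. The NLR moves only with differential failure, in either direction, and by about 0.01 at a 5% rate in one group.

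This rests on two assumptions: the failure rate, which the plan does not state, and that a patient without a valid DSI goes on to EGD without a repeat test. Section 6.3 gives a single exposure. The change is worth making because it is cheap, even though the effect is probably small.

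**What to change.** 1. Reconcile sections 6.6 and 9.3 on one definition of the primary analysis set, and state explicitly what happens to a subject with an EGD but no DSI. The complete-pair analysis can remain primary.
2. In section 9.3, replace the entry of no sensitivity datasets with one comprising all subjects in whom the SHUNT test was started and the EGD was done within the 42-day window. Count a subject without a valid DSI as DSI > 18.3, that is, not ruled out.
3. In section 9.4.2, specify that sensitivity, specificity and NLR are reported for this set, with the same score interval for the NLR as in the primary analysis. If EGDs avoided is reported, give it for both sets.
4. Tabulate failed tests and their reasons by large-varix status, so that differential failure can be seen.

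The cost is some SAP wording, one table and one additional analysis on data already collected. The downside for the sponsor is that reported specificity, and EGDs avoided if given, may be slightly lower.
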